2.4. Benefit/Risk Assessment

This is the first clinical study of duvelisib in subjects with R/M HNSCC and of duvelisib in combination with a PD-1 inhibitor.

As there are no clinical data for duvelisib in subjects with R/M HNSCC to date, the benefit/risk assessment for duvelisib reflects extensive clinical experience in subjects with hematologic malignancies who were treated with duvelisib ([COPIKTRA 2018](#)). The approved dose of each agent (duvelisib 25 mg BID PO; pembrolizumab 200 mg q3w IV) will be used for assessment of initial safety. As the maximal tolerated dose of duvelisib monotherapy is 75 mg twice daily (BID) in subjects with hematologic malignancies, which may suggest a relatively wide therapeutic window for duvelisib, such an approach is considered reasonable.

2.4.1. Risk Assessment

As the effect of duvelisib in subjects with R/M HNSCC is unknown, Stage 1 of the study includes a 1-week lead-in with duvelisib monotherapy to monitor for safety and biomarker sampling before the initiation of combination therapy with duvelisib and pembrolizumab.

For subjects with hematologic malignancies, clinical study results to date support a favorable benefit-risk assessment of duvelisib. The risks of duvelisib for subjects with hematologic malignancies are consistent with the adverse event (AE) profile for the PI3K inhibitor drug class and AEs experienced by patients undergoing treatment for advanced cancers. Important identified risks of duvelisib include infections, diarrhea/colitis, cutaneous reactions, pneumonitis, neutropenia, and alanine aminotransferase (ALT)/aspartate aminotransferase (AST) elevation. Potential risks include hepatotoxicity, drug-drug interaction (DDI), and reproductive toxicity. These toxicities are managed using a combination of prophylaxis, supportive care, and dose modifications. Guidance on management of these AEs, including duvelisib dose interruptions and modifications, is provided in Section 6.6 and Section 6.7. Detailed information about the known and expected risks and reasonably expected AEs of duvelisib may be found in the Investigator's Brochure (IB).

The identified risks of pembrolizumab ([Keytruda 2019](#)) are infusion reactions and the following immune-mediated conditions: pneumonitis, colitis, hepatitis, endocrinopathies, nephritis and renal dysfunction, and cutaneous adverse reactions (including rash). Refer to the pembrolizumab prescribing information for guidance on management of these AEs ([Keytruda 2019](#)).

Based on the monotherapy safety profiles for each drug, potential overlapping toxicities for duvelisib in combination with pembrolizumab include non-infectious diarrhea or colitis, cutaneous reactions, pneumonitis without suspected infectious cause, and elevations in ALT and AST levels (Section 6.6.1). These events will be closely monitored during the study.

Although duvelisib has not yet been evaluated in subjects with solid tumors, initial safety results for an ongoing first-in-human study of the oral selective inhibitor of PI3K- γ (IPI-549) in combination with nivolumab in patients with melanoma, non-small cell lung cancer (NSCLC), or HNSCC demonstrated favorable tolerability ([Sullivan 2018](#)).

2.4.2. Benefit Assessment

Subjects may derive benefit due to improvements in symptoms and tumor control. Duvelisib treatment produced clinical activity in subjects with hematologic malignancies, including CLL/SLL (approval), FL (accelerated approval), and peripheral T-cell lymphoma. More detailed information about the clinical efficacy observed in duvelisib studies can be found in the IB and the duvelisib prescribing information ([COPIKTRA 2018](#)).

Pembrolizumab has shown benefit in multiple solid tumor indications. Pembrolizumab is approved as a single agent for the first-line treatment of patients with metastatic or with unresectable, recurrent HNSCC whose tumors express PD-L1 (CPS ≥ 1) as determined by an FDA-approved test and is approved in combination with platinum and 5-FU for all patients with R/M HNSCC ([Keytruda 2019](#)). As presented in the pembrolizumab prescribing information ([Keytruda 2019](#)), results for the pre-specified interim analysis in the KEYNOTE-048 study of pembrolizumab as first-line treatment for patients with R/M HNSCC showed that compared with standard first-line treatment (i.e., EXTREME, consisting of cetuximab plus carboplatin or

cisplatin), pembrolizumab monotherapy had superior OS among patients whose tumors had PD-L1 CPS of ≥ 20 or ≥ 1 , and noninferior OS in the total population with favorable safety. Pembrolizumab is approved as a second-line treatment in patients with R/M HNSCC with disease progression on or after platinum-containing chemotherapy based on the ORR of 16% (complete response [CR] = 5%) and the DOR (2.41 months to 27.71 months; 23 of 28 responding patients [82%] had response durations of ≥ 6 months) in the KEYNOTE-012 study ([Keytruda 2019](#)).

In vivo data from nonclinical studies in solid tumor models, including an HNSCC (i.e., MOC1) model, support the hypothesis that the addition of duvelisib may improve the activity of PD-1 inhibitors in solid tumors (Section [2.3.1](#)).

Although duvelisib has not yet been evaluated in subjects with solid tumors, initial efficacy results from an ongoing study of an oral selective inhibitor of PI3K- γ (IPI-549) in combination with nivolumab in patients with melanoma, NSCLC, or HNSCC demonstrated early signs of clinical activity and evidence of immune modulation ([Sullivan 2018](#)). In this study, 2 patients had PR at first assessment (8 weeks) and 40% of patients (n = 12) remained on study ≥ 12 weeks.

It is anticipated that analysis of safety, tolerability, pharmacokinetics (PK), biomarker and preliminary efficacy data will help guide future development of duvelisib in combination with pembrolizumab in HNSCC.

2.4.3. Overall Benefit/Risk Conclusion

As early phase clinical studies are designed to provide information about the safety and efficacy of an investigational drug, subjects enrolled in the study cannot expect to receive a direct benefit from an experimental treatment.

Although pembrolizumab is approved for the treatment of patients with HNSCC, the ORR (19% for first-line treatment in patients with CPS ≥ 1 and 16% for second-line treatment) was relatively low ([Keytruda 2019](#)). Based on the strong antitumor synergy (i.e., inhibition of tumor growth and prolonged survival) for duvelisib in combination with a PD-1 inhibitor observed in the nonclinical in vivo studies and the manageable AE profile for duvelisib in patients with hematologic malignancies, subjects with R/M HNSCC could potentially benefit from improved response rates.

3. OBJECTIVES AND ENDPOINTS

Table 5: Objectives and Endpoints

Objectives	Endpoints (See Section 9.4 for definitions)
Stage 1 - Unique Objectives/Endpoints	
Primary	
Evaluate the safety and tolerability of duvelisib in combination with pembrolizumab in subjects with recurrent or metastatic (R/M) head and neck squamous cell carcinoma (HNSCC)	Safety and tolerability of study interventions based on dose-limiting toxicities (DLTs), adverse events (AEs), serious AEs (SAEs), vital signs, physical examinations, and clinical laboratory measurements
Secondary	
Characterize the overall response rate (ORR) of duvelisib in combination with pembrolizumab in subjects with R/M HNSCC	ORR, which includes partial response (PR) and complete response (CR) according to Response Evaluation Criteria in Solid Tumors (RECIST) v 1.1 (Eisenhauer 2009)
Stage 1 and Stage 2 – Combined Objectives/Endpoints	
Primary	
Characterize the ORR of duvelisib in combination with pembrolizumab	ORR, which includes PR and CR, according to RECIST v 1.1 (Eisenhauer 2009)
Secondary	
Characterize other efficacy parameters of duvelisib in combination with pembrolizumab	
 Duration of response (DOR), defined as time from response \geq PR to documented disease progression according to RECIST v 1.1 (Eisenhauer 2009) Progression-free survival (PFS), defined as the time from start of treatment to documented disease progression according to RECIST v 1.1 (Eisenhauer 2009), or death due to any cause Overall survival (OS), defined as the time from start of treatment to the date of death
Characterize the pharmacokinetics (PK) of duvelisib (and metabolite IPI-656) monotherapy and of duvelisib in combination with pembrolizumab	PK parameters for duvelisib (and metabolite IPI-656)
Evaluate the safety and tolerability of duvelisib in combination with pembrolizumab	Safety and tolerability parameters including AEs, SAEs, vital signs, physical examinations, and clinical laboratory measurements

Objectives	Endpoints (See Section 9.4 for definitions)
Exploratory	
Evaluate potential biomarkers for possible associations with clinical efficacy and/or safety outcomes of duvelisib in combination with pembrolizumab	
• Blood assessments of immune cell populations, chemokines, cytokines and circulating tumor DNA• Fecal assessments of protein, DNA, and/or RNA• Tumor biopsy evaluation of biomarkers such as gene and copy number variation, RNA expression, protein expression, and/or immune cell content (Required biopsies in Stage 1 and optional biopsy in Stage 2)• ORR and its relationship to tumor and/or immune cell programmed cell death ligand 1 (PD-L1) levels and to tumor human papillomavirus (HPV) status

4. STUDY DESIGN

4.1. Overall Design

This is a multicenter, non-randomized, open-label, Phase 1b/2 study of duvelisib in combination with pembrolizumab in subjects with R/M HNSCC who are eligible for pembrolizumab monotherapy based on the current pembrolizumab prescribing information ([Keytruda 2019](#)). This study will be conducted at multiple sites in the US and will include approximately 13 subjects in Stage 1 and 17 additional subjects in Stage 2, for a total of 30 subjects in the final analysis.

The study will follow a Simon two-stage design ([Simon 1989](#)).

The study stages are depicted in [Figure 1](#) and the treatment/imaging schemes for Stage 1 and Stage 2 are depicted in [Figure 2](#) and [Figure 3](#), respectively.

Subjects will receive duvelisib 25 mg BID orally (PO) in combination with pembrolizumab 200 mg every 3 weeks (q3w) intravenously (IV).

In **Stage 1**, subjects will have a 1-week lead-in with duvelisib before the initiation of combination therapy with duvelisib and pembrolizumab. Approximately 13 subjects are planned to be accrued in this stage. The first 6 subjects will be assessed for dose-limiting toxicities (DLTs). The DLT evaluation period will be Cycle 1 (4 weeks or 28 days): the 1-week duvelisib monotherapy lead-in period followed by 1 dose of pembrolizumab in combination with 3 additional weeks of continuous dosing of duvelisib. Every effort will be made to administer the first dose of pembrolizumab on Day 8 of Cycle 1 (C1D8). If the first dose of pembrolizumab on C1D8 is delayed, every effort should be made to delay the subsequent dosing of the next cycle (within the protocol-allowed window of 3 days) to achieve as close to a 3-week interval between pembrolizumab doses as possible. The Medical Monitor needs to be consulted for such adjustments to ensure uniformity of approach and to account for subject-specific circumstances. For example, if the third day of the C2D1 window falls on a weekend, an additional adjustment would need to be made on a case-by-case basis. In the event of a delay of the start of pembrolizumab therapy, DLTs will be evaluated at the end of the third week of combination therapy.

The DLT evaluation period will be used to assess DLTs in the first 6 subjects.

- If there is ≤ 1 DLT in the 6 DLT-evaluable subjects, additional subjects will be enrolled to bring the total dosed in Stage 1 to approximately 13 subjects.
- If there are ≥ 2 DLTs in the first 6 subjects, enrollment at duvelisib 25 mg BID will stop. Enrollment would restart at a reduced duvelisib dose (15 mg BID) to assess DLTs at the lower dose (dose level -1; see [Table 6](#)).

Table 6: Duvelisib Dose Levels

Dose Level	Duvelisib, mg BID PO
Starting Dose	25
-1	15

Abbreviations: BID: twice daily; PO: oral.

A formal analysis of available safety data will be conducted when the first 10 subjects treated have received at least 1 cycle of study treatment. This will enable assessment of toxicities of later onset, particularly outside of the DLT window.

If an excessive rate of Grade 3 or higher overlapping SAEs (defined as any rate for each SAE that is above the highest reported in warnings and precautions of the prescribing information for either duvelisib [COPIKTRA 2018] or pembrolizumab [Keytruda 2019], respectively), such as pneumonitis, colitis, cutaneous skin reactions, and elevations of AST/ALT, is observed outside of the DLT window, a decision for stopping or modifying the study may be made. However, recognizing that the observed rate of such events can be highly sensitive due to the small sample size, the totality of safety data will be reviewed and carefully considered prior to making a formal decision.

An interim analysis of ORR will occur after all of the planned 13 subjects in Stage 1 are enrolled, dosed, and have been followed through at least the first disease response assessment.

- If there are \leq 2 responses (CR or PR) in the 13 subjects in Stage 1, further accrual in the study may be stopped. However, all available data, including the relative proportion of CRs, will be analyzed before a final decision is made.
- If > 2 responses are observed in Stage 1, enrollment will continue in Stage 2.

In **Stage 2**, 17 additional subjects will be accrued for a total of 30 subjects in the final analysis. Subjects enrolled in Stage 2 will only receive combination therapy with duvelisib and pembrolizumab. Enrollment into Stage 2 may proceed prior to completion of the interim analysis as long as at least 2 of the 13 subjects enrolled in Stage 1 have a confirmed response.

The ORR and PFS will be assessed according to Response Evaluation Criteria in Solid Tumors (RECIST) v 1.1 (Eisenhauer 2009).

Subjects will be monitored continuously for safety while on study treatment. Adverse events will be classified using the National Cancer Institute Common Terminology Criteria for Adverse Events (NCI CTCAE) Version 5.0 or higher.

Higher doses of duvelisib may be explored in additional subjects via a protocol amendment, if warranted by observed data.

Subjects will be treated until documented progressive disease (PD) (Section 8.1.2), unacceptable toxicity (Section 6.6), discontinuation criteria are met (Section 7.1), withdrawal (Section 7.2), or death. The total duration of treatment will not exceed 24 months. After treatment discontinuation, subjects will complete an End of Treatment visit and will be followed for safety

for an additional 30 days. All subjects with treatment-related AEs/serious adverse events (SAEs) should be observed until resolution or stabilization.

It is anticipated that the study accrual will occur over approximately 18 months. All subjects will be followed for survival for 1 year after the last subject is enrolled and dosed.

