9.1. Statistical Hypotheses

This study will test the null hypothesis that the ORR is $\leq 16\%$ against the alternative that ORR is $\geq 44\%$. The ORR (proportion of subjects achieving CR or PR) according to RECIST v 1.1 ([Eisenhauer 2009](#)) will be estimated on the modified Intent-to-Treat (mITT) population (i.e., all subjects who receive at least 1 dose of duvelisib in combination with at least 1 dose of pembrolizumab). For this study "response" is defined as a confirmed response, per RECIST v 1.1 ([Eisenhauer 2009](#)), unless otherwise specified. Details for determination of confirmation of response will be provided in the SAP. A 2-sided exact 95% CI will be calculated.

The ORR of 16% being used for the null hypothesis is based on multiple sources. The pembrolizumab prescribing information ([Keytruda 2019](#)) reports an ORR for pembrolizumab monotherapy of 16% in subjects previously treated with a platinum-containing therapy in the KEYNOTE-012 study. An ORR of 16% is also reported for subjects naïve to anti-PD-L1 therapy in the KEYNOTE-055 study ([Bauml 2017](#)). Further, the ORR for pembrolizumab monotherapy is reported in the USPI as 19%. Therefore, an uninteresting response rate of 16% will be used for all subjects in this study.

The evaluation of the primary endpoint will be conducted at the highest dose that is tolerated during the DLT evaluation. Therefore, if the initial dose of 25 mg BID is not tolerated but the reduced dose of 15 mg BID is tolerated, the primary endpoint will be evaluated in all subjects starting at the tolerated dose.

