9.2. Sample Size Determination

The study will follow a Simon two-stage design ([Simon 1989](#)). In the first stage, approximately 13 subjects will be accrued. If there are 2 or fewer responses (CR or PR) in these 13 subjects, further accrual in the study may be stopped. However, all available data will be considered before termination.

In Stage 2, 17 additional subjects will be accrued for a total of 30 subjects in the final analysis. The null hypothesis will be rejected if 10 or more responses (CR or PR) are observed in 30 subjects. This design yields an overall type I error rate of 5% and power of 90% when the true response rate is 44%.

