9.4. Statistical Analyses

The SAP will be finalized before database lock and it will include a more technical and detailed description of the statistical analyses summarized in this section. This section is a summary of the planned statistical analyses of the most important endpoints, including primary and secondary endpoints.

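### The Stage 1 futility count may be taken before the last subjects' responses can be confirmed, and the supplied text does not say how a pending response counts

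*Combined protocol and SAP*

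**What the plan says.** **Timing.** Section 4.1 places the interim ORR analysis after all 13 planned Stage 1 subjects are "enrolled, dosed, and have been followed through at least the first disease response assessment". The Synopsis and Section 9.4.3 give the same timing. In Stage 1 the first assessment falls 10 weeks after the first duvelisib dose (Table 1; Section 8.1.1).

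**What a response is.** Under Section 9.1 a response "is defined as a confirmed response, per RECIST v 1.1", unless otherwise specified. Section 8.1.1 makes a confirmatory scan mandatory after a CR or PR and recommends it 4 (+1) weeks after the initial response. On the remaining rules, Section 9.1 says: "Details for determination of confirmation of response will be provided in the SAP". Section 9.4 sets the deadline for that document: "The SAP will be finalized before database lock". It sets no deadline relative to the interim.

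**The decision.** Section 9.2: "If there are 2 or fewer responses (CR or PR) in these 13 subjects, further accrual in the study may be stopped". Section 4.1 qualifies this: "However, all available data, including the relative proportion of CRs, will be analyzed before a final decision is made". With more than 2, "responses are observed in Stage 1, enrollment will continue in Stage 2".

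**The Stage 2 gate.** Section 4.1 and the Synopsis also let Stage 2 enrollment go ahead before the interim is complete, "as long as at least 2 of the 13 subjects enrolled in Stage 1 have a confirmed response".

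**The concern.** The timing rule and the response definition do not fit together at the earliest permitted date. On the day of the 13th subject's week-10 scan, a CR or PR first seen in that subject cannot have been confirmed. The same may hold for the one or more subjects dosed just before. The supplied text does not say whether such a response counts toward the boundary or whether the count waits for it. Because the SAP is tied only to database lock, nothing supplied requires this to be settled before the interim.

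One response can decide the outcome with 13 subjects. The 90% power presumes that the status of all 13 is known at the futility look. If pending responses were counted as non-responses, an active combination would be more likely to meet the stopping boundary.

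The gate adds a second ambiguity: exactly 2 confirmed responses in 13 both meet the futility boundary and permit Stage 2 to open.

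**Working it through.** **Inputs.** Null rate 16% (Section 9.1). From Section 9.2: alternative 44%, futility boundary 2 or fewer of 13, 17 further subjects, rejection at 10 or more of 30. First scan at week 10, confirmation 4 to 5 weeks later (Section 8.1.1). Accrual over about 18 months (Section 4.1).

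**Formulas.** Let k of the 13 be pending at the look. They are treated as non-responders for the futility rule but count normally in the final 30. With true rate p:

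- P(stop) = P(Bin(13−k, p) ≤ 2)
- P(reject) = Σ over x = 3 to 13−k of P(Bin(13−k, p) = x) × P(Bin(17+k, p) ≥ 10−x)

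**The plan's own figure (k = 0).** At 44%, P(stop) = 0.0005 + 0.0054 + 0.0256 = 0.032, and power is 90.04%. The stated 90% reproduces. The type I error is 1.4%, within the stated 5%.

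**With subjects pending.** For example, k = 2 gives P(stop) = 0.0017 + 0.0147 + 0.0577 = 0.074.

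| Pending k | P(stop) at 44% | Power at 44% | Type I error at 16% |
|---|---|---|---|
| 0 | 3.2% | 90.0% | 1.41% |
| 1 | 4.9% | 88.9% | 1.35% |
| 2 | 7.4% | 87.0% | 1.28% |
| 3 | 11.1% | 84.0% | 1.17% |
| 4 | 16.4% | 79.5% | 1.04% |

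With k = 2, 4.24 of the 7.40 percentage points of stopping probability (57%) come from trials that would reach 3 or more responses once the pending scans are read.

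**How many would be pending?** Only the 13th subject is certain, so k is at least 1. Evenly spaced accrual is an assumption: 18 × 52.18 / 12 / 30 = 2.61 weeks between subjects. When subject 13 has the week-10 scan, subject 12 is 2.6 weeks past that scan and subject 11 is 5.2 weeks past it. With confirmation at 4 or 5 weeks, k = 2. Other assumptions:

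- Subjects 4 or more weeks apart, with 4-week confirmation: k = 1.
- Confirmation only at the next 9-weekly scan, at 2.61-week spacing: k = 4, since 3 × 2.61 = 7.8 is below 9.
- Poisson accrual at the same mean rate: average power about 84.4% (4-week confirmation) or 82.7% (5-week).
- A 5-week lag between the 13th subject's scan and the data cut: power back to 90.0%.

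**The gate.** P(exactly 2 of 13) at 16% = 78 × 0.16² × 0.84¹¹ = 29.3%; at 44% it is 2.6%. With all statuses known, P(stop) at 16% is 65.4% if 2 responses stop the trial and 36.0% if 2 are enough to continue. If 2 confirmed responses are enough, power at 44% is 91.3%, 91.1%, 90.7%, 90.0% and 88.8% for k = 0 to 4.

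**Limit.** Responses first seen at week 19 or later are outside these figures.

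**The case against.** The strongest reply is that the protocol does not commit to the strict rule on which the loss depends. Accrual may be stopped rather than must be, and all available data are reviewed first; a PR awaiting its confirmatory scan is available data. The timing wording sets a minimum, so a later look is allowed. The interim bullets in Section 4.1 speak of responses observed, while the gate sentence in the same section says confirmed. Section 9.1 allows exceptions, so the futility count may be meant to use observed responses. The gate would also offset the loss if 2 confirmed responses sufficed to continue. Finally, no SAP text is in the supplied file and Figure 1 is not shown; either may settle the point.

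Most of this stands. A reader might infer that the design's power is really 87% and the stated 90% wrong. The documents do not support that: 90% is correct for the rule as specified, and 87.0% needs evenly spaced accrual, the earliest look, a strict confirmed count and no use of discretion.

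The reply does not remove the gap. Discretion does not say which count is compared with the boundary. Reading the bullets as unconfirmed responses is possible but not stated. Relying on the gate preserves power only by giving up much of the futility protection: P(stop) at 16% falls from 65.4% to 36.0% with all statuses known.

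**Conclusion.** The point holds as a conditional one. The earliest permitted look precedes the date on which the last subject's first-scan response can be confirmed, and the supplied text does not say how that response counts.

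The size is modest. Under a strict confirmed count on that date, power falls by 1.2 percentage points with the one subject certain to be pending (90.04 − 88.88) and by 3.1 with two (90.04 − 86.98, even accrual). It falls further with clustered accrual or later confirmation. Type I error does not rise. There is no loss if the team waits for the scans, weighs pending responses or counts observed ones. Continuing at 2 confirmed responses also offsets it with up to 3 pending.

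The overlap at exactly 2 of 13 is a separate inconsistency and has the larger effect on futility protection at 16%.

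**What to change.** In the Synopsis and Sections 4.1 and 9.4.3:

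1. Take the interim count once every CR or PR first seen at a Stage 1 subject's first assessment has had its confirmatory scan, or that subject has progressed or discontinued. Set a limit of 15 weeks after the 13th subject's first dose (10 + 4 + 1).
2. At that cut, treat as pending only a CR or PR whose confirmatory scan is still outstanding, and count it as a response for the futility rule only. One that failed confirmation, or whose subject progressed or discontinued, is not pending. The final analysis uses confirmed responses.
3. Reconcile the sentence opening Stage 2 at 2 or more confirmed responses with the boundary of 2 or fewer, and say which governs at exactly 2.

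**Cost.** The delay is at most about 5 weeks (15 − 10), and none if no CR or PR is pending. For responses first seen at week 10, power returns to 90.0% when the scans are done on time. The counting rule is needed because the scan window is only recommended: under a strict count, one outstanding scan still gives 88.9% and two give 87.0%.

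The chance of stopping an inactive regimen falls slightly. With u outstanding scans and an assumed apparent rate q at a true confirmed rate of 16%, P(stop) = P(Bin(13−u, 0.16) + Bin(u, q) ≤ 2). This gives 64.2% (u = 1, q = 20%) to 60.6% (u = 2, q = 24%), against 65.4%. The restriction in item 2 matters: if every unconfirmed CR or PR counted, P(Bin(13, q) ≤ 2) would be 50.2% at q = 20% and 36.4% at q = 24%. Type I error stays at about 1.4%.
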